#### 6.2.6 Health economic evaluation

A formal health economic evaluation will not be conducted in this feasibility study.

To assess the feasibility of the proposed health economic evaluation for the main trial, we will assess the level of completion of the EQ-5D-5L questionnaire at baseline and 3 months, and the level of completion and suitability of the patient resource use questionnaire at 3 months.

Overall response rates for each questionnaire will be calculated. Within questionnaire completion rates will also be calculated in order to assess the level of completion of specific questions. Assessment of appropriateness of completion will also be undertaken, with questions to be refined as necessary.

Data on opioid prescriptions and use will be available from patient self-report questionnaires and medical record review. This will allow comparison of the two data sources to determine the final method of data collection on opioids for the economic evaluation within the definitive trial.

# 6.2.7 Sample size estimate for a main trial

The following parameters will be calculated, along with a 95% confidence interval, to inform the sample size calculation for a main trial, however our interpretation will be cautious and will focus on the 95% confidence interval (rather than the point estimate) given the small number of clusters and sample size in the feasibility study.

- Intra-cluster correlation coefficient (ICC)
- Coefficient of variation (CV)
- Standard deviation (SD) of the BPI total score at baseline

### 6.2.8 Acceptability questionnaire data

The mean and standard deviation (SD) as well as the median and interquartile range (IQR) for the TFA questions and the acceptability/credibility questions will be calculated from items 1-8 and items 9-12 of the Acceptability Questionnaire respectively. These data will be considered alongside qualitative data as part of decision making regarding progression to a main trial. A mean score of  $\geq$  5/10 for each of items 9-12 will be considered the threshold for acceptability/credibility, as in the previous trials using this measure. 

### 6.3 Qualitative data analysis

Audio-recorded consultations and interviews will be professionally transcribed ad verbatim. The Framework approach to analysis will be used as this starts deductively from pre-set aims and objectives, and will enable a focused and efficient analysis within the timeframe of this study, and can be used within a multidisciplinary research team setting. Analysis will involve familiarisation, identification of a framework (including study aims, TDF, TFA and NPT) indexing, charting and mapping, and interpretation. Coding of transcripts will be undertaken by members of the research team from different professional backgrounds (including GPs and clinical pharmacists) to increase trustworthiness of the analysis. Continuous team analysis of data will help to challenge interpretations and coding will be refined and agreed through ongoing discussion. The approach described will allow for both

a-priori (TDF, TFA, NPT) and emergent codes to be identified. The data analysis will be facilitated using qualitative data-analysis software QSR NVivo.

# 6.4 Integrated analysis

When analysis of the quantitative and qualitative data is complete, a triangulation protocol will be used. This technique enables integration of data in order to investigate completeness, convergence, and dissonance of key themes across datasets. Methods include following a thread and development of a convergence coding matrix. The matrix allows findings from different study components to be displayed side by side. Integration will aid interpretation of findings and inform decisions about changes to trial processes or intervention components ahead of a full-scale trial. Feasibility of the proposed main trial design will be assessed from recruitment and retention rates to the research evaluation in patients taking up the PROMPPT intervention and uptake of PROMPPT by patients who do not participate in the research evaluation. Intervention acceptability/feasibility will be assessed by integrating findings from the process evaluation with rates of intervention uptake, attendance at follow-up appointments and acceptability/credibility scores.

# 6.5 Progression criteria

The findings will determine the extent of modification needed to the intervention, clinical pharmacist training and/or trial processes before proceeding to the main trial.

Criteria to progress to a main trial with no more than minor modifications are:

- Recruitment rate to MOPP: is ≥20% of eligible patients consent to participate
- >50% of MOPP participants attend at least one PROMPPT consultation
- ≥ 70% of MOPP participants complete 3-month follow-up questionnaires.
- Mean acceptability/credibility score (items 9-12 of the Acceptability Questionnaire) ≥ 5
- Evidence from interviews about intervention acceptability is in line with the TFA (e.g. PROMPPT is understandable/has coherence, is ethical, perceived as likely to achieve its purpose, does not place excess burden on participants and participants can and want to take part).

If these criteria are not met, discussions will follow in collaboration with the Programme Steering Committee to determine which elements of the intervention, training and/or trial processes need modification and these will be refined accordingly before proceeding to a main trial.

### 7 DATA HANDLING

### 7.1 Data collection tools and source document identification

Self-report questionnaires, clinical data collected on study specific case report forms (CRFs) audio-recordings (of consultations and interviews) and prescribing data from linked medical records will form the basis of the data collection. A dedicated study database will be

developed and maintained on a secure password protected network environment at Keele University Clinical Trials Unit (registered with UK Clinical Research Collaboration) and managed by a Senior Data Manager and will be the final repository for the data collection.

Each person will be allocated a unique study number on mailing of the baseline questionnaire, so that only anonymised data are used for analysis. The unique study numbers will be generated from the study database and provided to each practice for use when mailing. The number will be made up of site ID followed by a sequence of unique numbers. The study number will be for use on CRFs, other study documents and the electronic database. The documents will also use participants' initials (of first and last names separated by a hyphen) and date of birth (dd/mm/yy).

Questionnaires will include the participant's Study ID plus date of birth and gender to confirm the correct participant's study ID has been provided. Study data will be recorded on CRFs by clinicians or local research staff who are taking part in the study and will be trained in accordance with the protocol on completing CRFs. The study site is responsible for redacting all other personal identifiable data prior to CRFs and any other reports being sent to Keele CTU, where appropriate. Following receipt, Keele CTU will contact the site to resolve any missing or discrepant data queries relating to clinical data in accordance with Keele CTU procedures.

Medical records of participant's who consent to this part of the study, will be extracted and de-personalised at their GP surgery before being securely transferred to Keele Clinical Trials Unit. De-personalised medical records will be linked to the participant's Study ID and to other study data attributed to each participant.

Consultations and interviews will be electronically audio-recorded using a dictaphone provided by Keele University and the audio files will be securely transferred from study sites into Keele's Secure Network. We will be using audio devices commonly used for research purposes. Although the devices are not password protected, the device will not be left unattended at any point until the data is transferred to Keele University's password protected secure network. The recording will be kept on the device only whilst the researcher is travelling back to Keele University, and will be removed from the device as soon as possible.

# 7.2 Data handling and record keeping

Data management is by Keele CTU. A Data Manager based at the Keele University CTU will oversee all responsibilities delegated to the CTU for data management and data entered to the study database.

Completed self-report questionnaires will be returned to Keele CTU in pre-paid envelopes provided to participants. Questionnaires will be date stamped on receipt at Keele CTU. CRFs will be sent to the Keele CTU either electronically or in pre-paid envelopes provided to each centre. The CTU data administrator will enter questionnaire and CRF data on to the study database around the time that they are received. Following receipt of associated consent forms, audio files will be securely transferred from study sites into Keele CTU's Secure Network and then will be securely transferred from Keele CTU to a professional transcription company, who are contracted under strict terms of confidentiality, via a secure portal.

Transcripts will be password encrypted when being returned by the transcription company via email to Keele CTU and will then be securely uploaded back onto Keele's Secure Network and the email version deleted.

All data collected during the course of the study will be kept strictly confidential and will be handled and stored in line with the local NHS and Keele CTU Data Security procedures and Keele University's Health and Social Care Quality Management System's Standard Operating Procedures (HSCR SOPs), which are in accordance with the relevant Data Protection regulations and good practice guidelines.

Audit of data entry is undertaken for questionnaires and CRFs by Keele CTU following HSCR SOPs and the verification checks supported by the research team. For details on data protection systems, see Section 9.7.

### 7.3 Access to Data

Direct access to study-specific data only will be given to authorised representatives of the Sponsor to permit study monitoring and audit.

# 7.4 Data Sharing Agreements

Prior to the start of recruitment, a signed Organisation Information Document and model non-commercial study agreement (mNCA) will be in place between each site, and Keele University to ensure the safe and lawful process of data sharing across organisations, as required by the Health Research Authority (HRA). Audio files containing qualitative data will be securely shared with a professional UK based transcription company under the terms of a confidentiality and data sharing agreement.

The EQ-5D-5L will be used with permission from EuroQol under the terms of its Non-Commercial Research Licence. Similarly, the BPI will be used with permission from the developers. The Pain Self Efficacy Questionnaire is a free to use questionnaire that does not require permission from the developers.

Any requests for access to the data from anyone outside of the research team (e.g. collaboration, joint publication, and data sharing requests from publishers) will follow the Keele University's SOP on data sharing.

# 7.5 Archiving

At the end of the study, data will be securely archived in line with the Sponsor's (Keele University) HSCR SOPs for 10 years after submission of the End of Study Declaration. Data held by Keele CTU will be archived in the designated Keele CTU archive facility and site data and documents will be archived at the participating sites. Following a retention review, if the archived material is agreed to be destroyed, arrangements for confidential destruction will then be made. Archiving will be in accordance with Keele University.

### 8 MONITORING & AUDIT

# 8.1 Study Management

### **Sponsor**

Keele University as the sponsor is responsible for initiation, operationalisation and financial management of the study. These functions are devolved to Keele CTU as will be detailed in the Delegation of Sponsorship Functions agreement, as follows:

### **Chief Investigator (CI)**

The CI (CDM) has overall responsibility for the scientific quality and delivery of the study. The CI will also be responsible for safety reporting and escalation of reportable adverse events.

## **Associate Investigator (AI)**

The Associate Investigator (JA) will support the CI in the day-to-day conduct, co-ordination and management of the study, ensuring the study is delivered in line with this protocol.

### **Keele CTU**

The Study Sponsor, Keele University, delegates the management of the study to Keele CTU. Keele CTU will provide set-up and monitoring of study conduct to Keele University HSCR SOPs, and GCP, database and web application development and maintenance, protocol development, CRF design, study design, monitoring schedule and statistical analysis for the study. In addition, Keele CTU will support obtaining research ethics and governance approvals and site set-up, ongoing management including training, monitoring reports and promotion of the study. In association with the CI and AI, Keele CTU will be responsible for the day-to-day running of the study including study management and administration, database administrative functions, data management, safety reporting and all statistical analyses. Regular monitoring of study recruitment will be performed and intervention eCRFs will be monitored, against the study protocol for compliance.

#### **NIHR Clinical Research Networks**

NIHR CRNs will co-ordinate CRN support across the general practice sites and will provide funding or staff resource to secure the additional clinical time associated with service support to embed the study into the sites to allow identification of potentially eligible participants.

# **Study Management Group (SMG)**

The SMG, convened by the CI, will comprise members of the research team and Keele CTU and will have overall responsibility for the clinical set-up, promotion, ongoing management and monitoring of the study, and for analysis and interpretation of results. The AI (JA) will chair the SMG to oversee; obtaining regulatory approvals from the HRA and general practices; monitoring and managing funding; CRF development; protocol delivery; monitoring of recruitment, intervention delivery and follow-up procedures; data collection and database development; completion of regulatory reporting requirements; reporting of unexpected events to the REC, Programme Steering Committee (PSC) and Sponsor; and completing funder reporting requirements. The SMG will meet on a regular basis throughout the study.

# **Programme Steering Committee (PSC)**

This study forms part of a 5-year research programme. An independent PSC has been appointed according to the funder's (NIHR) requirements and has been approved by the NIHR. The PSC will provide overall supervision of the research programme according to agreed timelines. The PSC includes an Independent Chair (Professor of Primary Care and GP) and three additional independent members including; a statistician, a pharmacist, and a representative of patients and the public. The PSC will meet at agreed time points, at least annually, for the duration of the 5-year programme. The CI and AI will attend the PSC meetings to report on progress, together with other members of the research team, including the Lead Statistician and Lead Qualitative Researcher, as appropriate. Since this is a feasibility study with no planned interim statistical analysis, a data monitoring committee has not been formed and the PSC will take responsibility for monitoring study progress, adherence to protocol, participant safety and consideration of new information relevant to the research question and study design.

# 8.2 Monitoring arrangements

Monitoring will be conducted according to a Study Monitoring Plan developed by the SMG based on the study risk assessment and in accordance with Keele CTU and Sponsor SOPs, and agreed by the PSC. Monitoring will also be undertaken by the approving Research Ethics Committee (REC) in the format of annual progress reports, and the funder in the format of progress reports as required by the NIHR Programme Grants for Applied Research funding stream.

# 8.3 Safety Reporting

### **Adverse events**

A Serious Adverse Event (SAE) is defined by the Health Research Authority (HRA) as an untoward occurrence that:

- (a) results in death;
- (b) is life-threatening;
- (c) requires hospitalisation or prolongation of existing hospitalisation;
- (d) results in persistent or significant disability or incapacity;
- (e) consists of a congenital anomaly or birth defect; or
- (f) is otherwise considered medically significant by the investigator.

A SAE occurring to a research participant must be reported to the REC where in the opinion of the CI the event was: "Related" that is, it resulted from administration of any of the research procedures, and "Unexpected" that is, the type of event that is not an expected occurrence as a result of the intervention provided.

The potential harms of this feasibility study are considered to be minimal. The clinical management recommendations given to participating clinical pharmacists and GPs in participating practices are considered not only to be evidence-based best practice but also have strong clinical community endorsement and credibility.

### **Safety Reporting Exceptions**

The following expected adverse events will not be collected; transient increase in pain and /or withdrawal symptoms following opioid dose reduction that the participant feels able to manage without requirement for healthcare consultation.

# **Safety Reporting Process**

In addition to participant self-report, we will ask study clinicians (mainly clinical pharmacists) to report related and/or unexpected adverse events and SAEs if they become aware of them during the study. Similarly, if the participant's GP becomes aware that a SAE has occurred we will request that this is reported, as detailed in the letter informing them that their patient is participating in the study. Reporting procedures will be made clear during the protocol study training and will be contained in site files for all clinicians involved in the study.

Clinicians in participating practices will be asked to record events or concerns about the safety of subjects that arise as a result of the study, even if these events or concerns do not meet the definition of a serious adverse event requiring notification to the regulatory authorities.

All SAEs occurring from the point at which participants consent to participation in the MOPP study must be notified to the study Sponsor:

- via [contact] within 24 hours of the study clinicians becoming aware of the event AND
- via email [contact]

The Study CI or AI will be asked to assess SAE causality.

Any follow-up information should be sent to the Sponsor via the Study Team as it is available, and where appropriate. Events will be followed up until the event has been resolved or a final.

Once a SAE is identified and reported, this information is to be passed to the Study Manager who will ensure that the necessary paperwork is completed and will inform the CI. In line with Keele University's HSCR SOPs the reporting clinician will give their assessment and the CI will assess whether the event is related to or resulted from any of the study procedures or interventions and expectedness, according to the process laid out in Keele University's HSCR SOPs. Any SAE considered to be related to the study procedures will be reported to the REC and the PSC Chair by the CI within 15 calendar days of becoming aware of the event. All related or unexpected SAEs will also be reported to the study sponsor.

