### Sponsor

- Expedited reporting of Related Unexpected SAEs to the main REC.
- Reporting of confirmed related and unexpected SAEs to the Health Research Oversight Committee (HROC) in accordance with their requirements.

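### Section 8.3 gives conflicting rules on which related SAEs go to the ethics committee (REC), who sends them and by when

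*Protocol*

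**What the plan says.** Three places in section 8.3 of the protocol deal with reporting SAEs to the REC.

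- **Adverse events.** "A SAE occurring to a research participant must be reported to the REC where in the opinion of the CI the event was" both related and unexpected. The second condition is defined there: "that is, the type of event that is not an expected occurrence as a result of the intervention provided".
- **Safety Reporting Process.** "Any SAE considered to be related to the study procedures will be reported to the REC and the PSC Chair by the CI", and this is to be done "within 15 calendar days of becoming aware of the event". Expectedness is not a condition.
- **Responsibilities for safety reporting, Sponsor list.** "Expedited reporting of Related Unexpected SAEs to the main REC". No number of days is attached, and the PSC is not mentioned.

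For reports to the Sponsor, Safety Reporting Process states: "All SAEs occurring from the point at which participants consent to participation in the MOPP study must be notified to the study Sponsor". The limit is 24 hours from the study clinicians becoming aware. The same subsection closes with: "All related or unexpected SAEs will also be reported to the study sponsor".

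**The concern.** These are operative safety instructions. An SAE judged related but of an expected type must go to the REC under one subsection and need not go under the other two. An SAE that is both related and unexpected has two named senders, the CI and the Sponsor, and only the CI has a deadline. It could be filed twice, or one party could rely on the other.

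The PSC Chair's notification is tied to the same sentence. Section 8.1 explains that no data monitoring committee was formed and that the PSC takes responsibility for participant safety. Within section 8.3, the PSC Chair is told of an SAE only through the CI sentence. If the narrower criterion is followed, or the Sponsor files instead of the CI, nothing else in section 8.3 prompts that notice.

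**Working it through.** No sample size, power or error rate is involved, so there is no figure to reproduce. The check applies each rule to the four possible SAE classes.

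**Reporting to the REC**

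| SAE class | Adverse events | Safety Reporting Process | Sponsor list |
|---|---|---|---|
| Related, unexpected | required | required, CI, 15 calendar days | required, Sponsor, no number of days |
| Related, expected | not required | required, CI, 15 calendar days | not listed |
| Unrelated, unexpected | not required | not required | not listed |
| Unrelated, expected | not required | not required | not listed |

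The three places agree on both unrelated classes. For related and unexpected SAEs they agree that a report is due, but not on who sends it or by when. For related and expected SAEs they disagree on whether a report is due at all.

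**Can the related, expected class occur?** Safety Reporting Exceptions treats a passing rise in pain, or withdrawal symptoms, after an opioid dose reduction as expected. It exempts these from collection only when the participant can manage without a healthcare consultation. If such an event led to hospital admission, it would meet the hospitalisation limb of the SAE definition and fall outside the exemption. It could then be judged related and of an expected type. That judgement is an assumption here, since the protocol does not say how such a case would be classified.

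**Reporting to the Sponsor.** Under the all-SAE rule, every class is notifiable within 24 hours. The closing sentence covers SAEs that are related or unexpected. A related SAE, expected or not, satisfies both sentences, so it reaches the Sponsor whichever is followed.

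**Who sends.** Section 8.1 makes the CI responsible for safety reporting and for escalating reportable events. It also makes the clinical trials unit (CTU), in association with the CI and Associate Investigator, responsible for safety reporting. It refers to a delegation agreement that is not part of the protocol. None of this text says that the CI or the CTU makes the REC report on the Sponsor's behalf. Section 8.1 also describes the Study Management Group as overseeing "reporting of unexpected events to the REC, Programme Steering Committee (PSC) and Sponsor". That wording has no relatedness or seriousness condition, but it is a summary of an oversight role and is not relied on here.

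**The case against.** The strongest reply is that the rules are nested. Adverse events states what must be reported and does not forbid reporting more, so a CI who follows Safety Reporting Process also meets the narrower criterion. That subsection has a named actor and a clock, and section 8.1 supports the CI as the person who escalates. The Sponsor list is brief, and the sponsor's operating procedures, the delegation agreement and the monitoring plan may settle who files. The class in dispute may also be very small.

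Part of this stands. A CI who follows the broadest wording leaves no related SAE unreported to the REC, and the unseen documents may resolve the sender. But the protocol nowhere says that the broadest wording prevails or that the Sponsor's duty is delegated to the CI. Someone working from either of the other two subsections reaches a different answer.

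A reader might infer more than the text supports on three points.

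- **Sponsor reporting is narrowed.** The closing sentence of Safety Reporting Process adds a report (it says also). It does not restrict the all-SAE rule, and it follows the CI's assessment, so it can be read as a second report after that step. It is redundant rather than contradictory.
- **Clinicians are told to withhold some SAEs.** The request to study clinicians reads naturally as related and/or unexpected adverse events, plus all SAEs. That agrees with the 24-hour rule. The next sentence asks GPs to report an SAE with no relatedness condition.
- **Causality has conflicting assessors.** An assessment by the reporting clinician followed by one from the CI, with the Associate Investigator able to act, is a two-level process and not a contradiction.

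**Conclusion.** The protocol contradicts itself on REC reporting in two respects. The event criterion is related and unexpected in two places and related alone in a third. The sender and time limit are the CI with 15 calendar days in one place and the Sponsor with no number of days in another. One of the four SAE classes therefore gets opposite answers, and one has two named senders.

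A reader might conclude that a related SAE could go wholly unreported. The text does not support that, because related SAEs reach the Sponsor under every rule in Safety Reporting Process. The exposure is confined to the REC and PSC Chair steps. That one party might leave the filing to the other is a possibility the wording allows, not something the protocol shows would happen.

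The number of events affected is unknown. The study plans 80 participants, and the protocol considers its potential harms minimal. No feasibility estimate or progression criterion depends on this point. It still merits correction, because it concerns participant safety and is cheap to put right. The conclusion rests on the protocol text alone; the operating procedures and the delegation agreement were not available.

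**What to change.** Reconcile the three places in section 8.3 (Adverse events, Safety Reporting Process and the Sponsor list) so that REC and PSC Chair reporting has:

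1. one event criterion, worded identically wherever it appears;
2. one responsible role, with any delegation from the Sponsor to the CI or the CTU stated;
3. one time limit in days.

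Which criterion, role and limit to adopt is for the sponsor and the CI to decide. Carry the agreed wording into the site training and site files.

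As tidying only, delete the closing sentence on related or unexpected SAEs going to the Sponsor, or state that it means a further report after the CI's assessment. Beside the all-SAE 24-hour rule it otherwise adds nothing.

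The cost is amendment wording and one line of training material. Data collection and analysis do not change.
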